6.3.5.3 Pain Relapse From 2 to 48 Hours Postdose During the DBT Phase

Pain relapse from 2 to 48 hours post DB dose is defined as migraine headache pain intensity of mild, moderate, or severe at any time point after 2 hours postdose for subjects with migraine headache pain intensity of none at 2 hours postdose. Thus, analyses of pain relapse are based on the DBT efficacy analysis set with pain freedom at 2 hours postdose in the DBT Phase.

Subjects who meet all the following criteria are classified as nonrelapsers:

- Migraine headache pain intensity of none at all time points after 2 hours postdose, i.e., in the 3 to 48-hour postdose analysis windows
- Missing migraine headache pain intensity at ≤ 1 time point only from 3 to 8 hours postdose, i.e., in the 3, 4, 6, or 8-hour postdose analysis window
- No rescue medication taken at or before the migraine headache pain intensity measurement in the 48-hour postdose analysis window (see Section 7.5).

Subjects who are not nonrelapsers are classified as relapsers. Relapse criteria include any of the following:

- Rescue medication taken at or before 48 hours postdose (RM=F; see Section 7.5)
- Mild, moderate, or severe migraine headache pain intensity at any time point after 2 hours postdose, i.e., in the 3, 4, 6, 8, 24, or 48-hour postdose analysis window
- Missing migraine headache pain intensity at 24 or 48 hours postdose (NC=F), i.e., in the 24 or 48-hour postdose analysis window
- Missing migraine headache pain intensity at >1 time point from 3 to 8 hours postdose (NC1=F), i.e., in the 3, 4, 6, or 8-hour postdose analysis window.

The percentage of subjects with pain relapse at 2 hours postdose during the DBT Phase is compared between treatment groups using analogous methods as the main analysis of the primary endpoint with NC1=F and RM=F (see Section 6.3.2.1). However, the RM=F method uses both criteria to classify subjects as failures (see Section 7.5).

In addition, the rate of rescue medication taken at or before 48 hours postdose (i.e., “n/N” and percentage) and 95% CI are also displayed by randomization stratum and overall for each treatment group.

Results support exploratory objective #10.

6.3.5.4 *Acute Migraine Medication Days per Month During the OLE Phase*

Analyses are based on the OLE migraine analysis set.

Acute migraine medication days are defined in Section 9.2.1.1.

Months in the OLE Phase are defined in Section 6.3.4.1.

The number of acute migraine medication days per month is prorated to 28 days and derived as follows:

- Month (i.e., 4-week interval) in the OLE Phase analysis period: $28 \times (\text{total number of acute migraine medication days in the month}) / (\text{time in the month})$. Subjects must have time in the specified month ≥ 14 days to be evaluable.
 - Time in Month X of the OLE Phase is defined as $\text{maximum}(\text{minimum}[Y, 28], 0)$, where $Y = \{\text{time in the OLE Phase}\} - (28 \times [X - 1])$ days and $X = 1, 2$, or 3 .
 - Time in the OLE Phase (days) is defined in Section 6.2.6.1.
- Overall OLE: $28 \times (\text{total number of acute migraine medication days in the OLE Phase analysis period through OLE day 84}) / \text{minimum}(\text{time in the OLE Phase}, 84 \text{ days})$.

The table of values for the number of acute migraine medication days per month in the OLE Phase is provided for the OLE migraine analysis set by treatment group/OL rimegepant and overall, and summaries parameters descriptively as continuous variables in each month of the OLE Phase and overall OLE. Results support exploratory objective #12.

The table of values for the number of acute migraine-specific medication days per month in the OLE Phase is provided analogously. Acute migraine-specific medication days are defined in Section 9.2.1.2. The number of acute migraine medication days per month is prorated to 28 days and derived analogously.

6.3.5.5 *Rescue Medication Use After Each of the First 5 Qualifying Migraine Attacks During the OLE Phase*

The percentage of subjects with rescue medication use is assessed for the first 5 qualifying migraine attacks ≥ 23 hours apart in the OLE Phase analysis period for the OLE efficacy analysis set.

The table displays the rate (i.e., “n/N” and percentage) of rescue medication use, ASE, and 95% CI by treatment group/OL rimegepant and overall after each qualifying migraine attack.

A qualifying migraine attack is defined as a migraine attack of moderate or severe migraine headache pain intensity that is first treated with study drug.

First, the first 5 qualifying migraine attacks ≥ 23 hours apart in the OLE Phase are determined analogously to the first 5 EQMAs ≥ 23 hours apart in the OLE Phase, but regardless of 24-hour postdose MQoL data (see Section 9.3.1). Next, the reported OL rimegepant date/time (to which a given qualifying migraine attack is linked) is used to determine whether OLE rescue medication is used after that qualifying migraine attack (see Section 6.2.6.3).

Results support exploratory objective #13.

6.4 Safety

Safety analyses are based on the safety analysis set, unless otherwise noted. Safety parameters include the following: deaths; AEs; laboratory tests; vital signs; physical measurements; electrocardiograms (ECGs); and C-SSRS.

Tables of safety endpoints are provided according to safety analysis period and analysis sets:

- On-DBT safety for the DBT safety analysis set by treatment group
- Post-DBT pre-OL rimegepant safety for the interim safety analysis set by treatment group and overall
- On-OL rimegepant safety for the OL rimegepant safety analysis set by treatment group/OL rimegepant and overall
- Follow-up safety for the follow-up safety analysis set by treatment group/OL rimegepant status and overall.

Results are presented by as-treated treatment group according to Section 6.1.1.1.

Measurements are slotting safety parameters into analysis periods.

Select safety parameters are tabulated descriptively as continuous variables at baseline and each scheduled visit over time during the on-DBT and on-OL rimegepant safety analysis periods. Measurements are slotted into analysis periods and analysis visits using the following steps:

- 1) Measurements are slotted into the Screening Phase, DBT Phase, OLE Phase, and Follow-up Phase analysis periods.
- 2) Measurements are slotted into analysis visits in the analysis periods listed in the previous step.
- 3) Measurements are slotted into safety analysis periods (pretreatment, on-DBT, or on-OL rimegepant, or follow-up).

See Sections 6.2.5, 7.2, and 7.3 for definitions of baseline, analysis periods, and analysis visit windows, respectively.

6.4.1 Adverse Events

Refer to the Core SAP for the following: AE start and end date imputation; death date derivation; counting and rounding rules in AE frequency tables; definitions of AEs related to study drug and significant AEs; and TLF contents.j

Frequency tables of AEs by SOC and PT display AEs in descending order of overall frequency within SOC and PT, unless otherwise specified.

The by-subject listing of AEs is provided for the enrolled analysis set.

6.4.1.1 Deaths

Deaths are identified from any of the following sources:

- AE CRF with any of the following: PT or reported term of “death”; outcome of “fatal”; “yes” response to any death-related question (e.g., “Did the AE result in death?”; “Is a death certificate available?”; “Is an autopsy report available?”); complete or partially complete death date.
- DB Subject Status CRF with any of the following: death as reason for DBT Phase non-completion; death as reason for not continuing to the OLE Phase (see Section 6.2.3.3.)
- OLE Subject Status CRF with any of the following: death as reason for OLE Phase non-completion; death as reason for not continuing to the Follow-up Phase.

The by-subject listing of deaths is provided for the enrolled analysis set.

6.4.1.2 AE Overviews

An AE overview frequency table displays the following categories without SOC and PT: any AE; AE related to study drug; AE leading to study drug discontinuation; SAE; SAE related to study drug; medication-overuse headache AE; hepatic-related AE; hepatic-related AE leading to study drug discontinuation; potential drug abuse AE; cardiovascular AE; suicidality AE; hypertension AE; and Raynaud’s phenomenon AE.

AE overview frequency tables are provided for the following safety analysis periods and analysis sets:

- On-DBT for the DBT safety analysis set
- On-DBT for the DBT safety analysis set by subgroup level and overall for all high-level safety subgroups of interest described in Section 4.3.2 for each treatment group. Results support exploratory objective #17.
- Post-DBT pre-OL rimegepant for the interim safety analysis set
- On-OL rimegepant for the OL rimegepant safety analysis set

- On-OL rimegepant for the OL rimegepant safety analysis set by subgroup level and overall for all high-level safety subgroups of interest specified in Section 4.3.2. Results support exploratory objective #17.
- Follow-up for the follow-up safety analysis set.

6.4.1.3 On-DBT AEs

Frequency tables of on-DBT AEs are provided for the DBT safety analysis set by SOC and PT for the following endpoints:

- AEs by worst intensity (other secondary objective #4) *
- AEs related to study drug by worst intensity
- SAEs (other secondary objective #4)
- Hepatic-related AEs (exploratory objective #13)
- Potential drug abuse AEs, displayed in alphabetical order by worst intensity and PT without SOC
- Cardiovascular AEs
- Suicidality AEs
- Hypertension AEs
- Hypertension AEs for subjects with medical history of hypertension.

Frequency tables of on-DBT AEs by SOC and PT display AEs in descending order of rimegepant frequency within SOC and PT.

Frequency tables of endpoints marked with “*” are also provided by subgroup level and overall for all high-level safety subgroups of interest specified in Section 4.3.2 for each treatment group. Results support exploratory objective #17.

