9.3.2. Safety Analyses

Deaths will be listed regardless of onset for the enrolled analysis set.

The frequencies of safety endpoints will be assessed descriptively as the number and percentage of subjects with events/findings separately for the 2 safety analysis sets (DBT and OL rimegepant).

The frequencies of the following safety endpoints will be tabulated on treatment: AEs by intensity (mild, moderate, severe, total); AEs related to study drug ; SAEs; AEs leading to study drug discontinuation; CV AEs by intensity; grade 3 to 4 laboratory test abnormalities; and LFT elevations based on fold changes above ULN, including ALT or AST >3x ULN concurrent (i.e., on the same laboratory test collection date) with total bilirubin >2x ULN.

The Investigators will determine the intensity of AEs and the relationship of AEs to study drug. The Investigators' terms will be coded using the latest version of the Medical Dictionary for Regulatory Activities (MedDRA) available at the start of the study. AEs will be tabulated by system organ class and preferred term. In tables by intensity, if a subject has an AE with different intensities over time, then only the greatest intensity will be reported.

Laboratory test results will be graded according to numeric laboratory test criteria from the following toxicity grading scales:

- Common Terminology Criteria for Adverse Events (CTCAE) Version 5.0 (2017). If CTCAE numeric test criteria are not available for a laboratory test, then numeric test criteria from Division of AIDS (DAIDS) Table for Grading the Severity of Adult and Pediatric Adverse Events Corrected Version 2.1 (2017) will be used.
- Food and Drug Administration (FDA) Toxicity Grading Scale for Healthy Adult and Adolescent Volunteers Enrolled in Preventive Vaccine Clinical Trials (2007).

If a subject has a laboratory test abnormality with different toxicity grades over time, then only the highest toxicity grade will be reported.

In addition, Quality Tolerance Limits (QTLs) are predefined parameters that are monitored during the study. Important deviations from the QTLs and any remedial actions taken will be summarized.

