Intercurrent Events	Rescue medication use: treatment policy strategy Nonrescue acute headache medication use: treatment policy strategy Prophylactic migraine medication use: treatment policy strategy Study drug discontinuation: treatment policy strategy
Objective 16	Frequency of LFT elevations based on fold changes above ULN in subjects treated with rimegepant during the DBT and OLE Phases
Safety Endpoint	Number and percentage of subjects with LFT elevations (ALT, AST, or TBL) based on fold changes above ULN on treatment during the DBT and OLE Phases
Summary	Frequency (1) by treatment group on DBT for the DBT safety analysis set with LFT data, and (2) treatment group and overall on OL rimegepant for the OL rimegepant safety analysis set with LFT data
Intercurrent Events	Rescue medication use: treatment policy strategy Nonrescue acute headache medication use: treatment policy strategy Prophylactic migraine medication use: treatment policy strategy Study drug discontinuation: while-on-treatment strategy
Objective 17	Primary and key secondary efficacy endpoints during the DBT Phase and high-level safety endpoints during the DBT and OLE Phases by history of clinically relevant CV disease (yes, no)
Efficacy and Safety Endpoints	
 Efficacy endpoints: see Table 1 and Table 2 Safety endpoints: see Table 3 Objective 4; also the number and percentage of subjects with AEs related to study drug by intensity on treatment during the DBT and OLE Phases
Summary	
 Efficacy endpoints: see Table 1 and Table 2 Safety endpoints: see Table 3 Objective 4
Intercurrent Events	
 Efficacy endpoints: see Table 1 and Table 2 Safety endpoints: see Table 3 Objective 4
Objective 18	Primary and key secondary efficacy endpoints during the DBT Phase by history of documented failure to ≥ 2 triptan medications with ≥ 1 failure due to lack of efficacy (yes, no)
Efficacy Endpoints	See Table 1 and Table 2.
Summary	See Table 1 and Table 2.
Intercurrent Events	See Table 1 and Table 2.

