4.3.2 Safety Subgroups

The following safety subgroups are of interest for high-level safety and supportive endpoints for the DBT and OL rimegepant safety analysis sets:

- Imputed randomization stratum: history of clinically relevant CV disease (yes or no; see Section 6.2.5.1).

Medical history of hypertension is a safety subgroup of interest for hypertension-related safety endpoints for the DBT and OL rimegepant safety analysis sets (see Section 6.2.5.3). Refer to the Core SAP for the subgroup definition.

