6.4.1.5 On-OL Rimegepant AEs

Frequency tables of on-OL rimegepant AEs are provided for the on-OL rimegepant analysis set by SOC and PT for the following endpoints:

- AEs by worst intensity (other secondary objective #4) *
- AEs related to study drug by worst intensity

- SAEs (other secondary objective #4)
- AEs leading to study drug discontinuation (other secondary objective #4)
- Hepatic-related AEs (exploratory objective #13)
- Hepatic-related AEs leading to study drug discontinuation (exploratory objective #14)
- Potential drug abuse AEs, displayed in alphabetical order by worst intensity and PT without SOC
- Cardiovascular AEs
- Suicidality AEs
- Hypertension AEs
- Hypertension AEs for subjects with medical history of hypertension.

Frequency tables of endpoints marked with “*” are also provided by subgroup level and overall for all high-level safety subgroups of interest specified in Section 4.3.2. Results support exploratory objective #17.

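### The SAP lists cardiovascular AEs without the intensity that the protocol names, and does not generate the drug-related AE intensity table by CV history that its own Objective 17 includes

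*SAP*

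**What the plan says.** Protocol 9.3.2 lists the safety endpoints to be tabulated on treatment. The list includes "SAEs; AEs leading to study drug discontinuation; CV AEs by intensity; grade 3 to 4 laboratory test abnormalities".

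SAP 6.4.1.3 (on-DBT) and 6.4.1.5 (on-OL rimegepant) list the AE tables by system organ class (SOC) and preferred term (PT). In both, the cardiovascular entry reads only "Cardiovascular AEs". Other bullets in the same lists do specify intensity: all AEs, drug-related AEs, and "Potential drug abuse AEs, displayed in alphabetical order by worst intensity and PT without SOC".

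Both sections use an asterisk to mark tables repeated by subgroup. In 6.4.1.3 the marked tables "are also provided by subgroup level and overall for all high-level safety subgroups of interest specified in Section 4.3.2 for each treatment group"; 6.4.1.5 has the equivalent sentence. SAP 4.3.2 defines that high-level safety subgroup as history of clinically relevant CV disease, yes or no. Only the all-AE intensity table carries the mark.

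SAP Table 4, Objective 17 covers safety by CV history. For its endpoints it refers to Table 3, Objective 4 and adds: "also the number and percentage of subjects with AEs related to study drug by intensity on treatment during the DBT and OLE Phases".

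**The concern.** Two statements of what will be tabulated are not matched by the table list that a programmer would work from. One is in the protocol and one is in the SAP's own estimand table.

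The subject matter makes this worth correcting. The trial enrols people unsuitable for triptans, and CV contraindication is one route to eligibility. CV history is the stratification factor and the high-level safety subgroup. If few CV AEs occur, a single grouped count that does not separate mild from severe gives the reader little. Under Objective 17, a reader of the report would also expect to see whether drug-related AEs were more intense in subjects with CV history, and would find only a count.

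**Working it through.** No figure in the plan bears on this point, so the check sets the passages side by side.

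**Step 1. CV AEs by intensity.** What each planned output gives:

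- Grouped CV AE table (SAP 6.4.1.3, 6.4.1.5): SOC and PT; no intensity stated; not marked for CV history.
- AE overview (SAP 6.4.1.2): one CV AE row, without SOC, PT or intensity; produced overall and by CV history, on-DBT and on-OL.
- All-AE table (SAP 6.4.1.3, 6.4.1.5): worst intensity by SOC and PT; produced overall and by CV history in both periods.
- AE listing (SAP 6.4.1) and narrative identifiers (SAP 6.4.6): subject level, not tabulations.

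None of these gives the number of subjects whose worst CV AE was mild, moderate or severe.

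**Step 2. Can that count be recovered from the all-AE table?** Not reliably. A subject with one mild and one severe CV term adds one to a mild PT row and one to a severe PT row, but belongs only in the severe category of the grouped count. Adding PT rows therefore counts that subject twice and overstates the mild category. An SOC row would serve only if the CV grouping coincided with a single SOC. Neither document defines the grouping, so that cannot be assumed.

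**Step 3. Objective 17, item by item, by CV history:**

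- AEs by intensity: delivered by the marked all-AE table.
- SAEs: counted in the AE overview by CV history.
- AEs leading to discontinuation: counted in the AE overview by CV history.
- Grade 3 to 4 laboratory abnormalities: delivered by the subgroup tables in SAP 6.4.2.1.
- Drug-related AEs by intensity: the overview gives a count without intensity, and the intensity table is unmarked in both sections. Not delivered.

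**Step 4. Is either omission a recorded decision?** The SAP revision history describes AE table changes in detail, including the change to worst intensity and the addition of hypertension AE tables. It does not record removing intensity from the CV AE table, and it does not explain the missing mark. The protocol's summary of changes shows that 9.3.2 was edited in the current version to align with the SAP, yet the CV intensity item stands in the current text. SAP Versions 3 to 6 are all based on that protocol version.

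**Size.** Two outputs × two periods (on-DBT and on-OL) = four table specifications. Two change an existing table and two add a subgroup version of one.

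**The case against.** The strongest reply has four parts.

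1. *The SAP may differ from the protocol.* Protocol section 9 allows this and requires an amendment only for major changes to the primary endpoint definitions or analyses. This stands as permission. It does not show that a change was intended, and it does not touch the conflict inside the SAP over Objective 17.

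2. *The details may be elsewhere.* SAP 6.4.1 leaves AE table contents and counting rules to the Core SAP, and SAP 6.1.1 leaves templates to a mock document. Neither was available, and intensity columns for CV AEs could be specified there. This limits the first part of the point. It has less force for the second, because the asterisk rule is set in this SAP.

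3. *The information is largely present.* This is correct and limits the size. A reader might infer that the SAP summarises neither CV AE severity nor CV AEs by CV history. The documents do not support that, given the outputs in Step 1. SAEs also have their own table, and non-serious CV AEs on rimegepant or in follow-up are flagged for narratives. Only the grouped intensity count is missing.

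4. *Objective 17 does not ask for CV AEs.* Also correct. A reader might infer that the dedicated CV AE table must be broken down by CV history. Neither document says so: protocol 9.3.2 asks for intensity only, and CV AEs are not among the Objective 17 endpoints. Nor do the documents require the on-OL CV AE table in the report at primary completion. SAP 8.2 produces every SAP table for the final report.

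The small CV stratum might also be offered as a measure of the harm. The cap allows at most 0.15 × 600 = 90 randomised subjects with CV history, about 45 per arm if split evenly. That suggests few events, but it is the same whether or not intensity is tabulated.

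**Conclusion.** The point holds as a table-specification mismatch with two parts. First, the protocol names CV AEs by intensity, and the SAP lists the grouped table without it in both treatment periods. Second, the SAP's Objective 17 includes drug-related AEs by intensity by CV history, and the asterisk rule does not generate that table in either period. No reason is given for either.

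The consequence is modest: four table specifications, all descriptive, with partial information in other outputs. No primary or key secondary analysis is affected, and no clinical-management question arises. It should still be corrected, because a programmer following the list would not produce a tabulation named in the protocol or one named in the SAP's own estimand table.

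This rests on two assumptions: that the Core SAP and mock tables do not already add CV intensity, and that the CV grouping is not a single SOC whose row would supply the count.

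**What to change.** In SAP 6.4.1.3 and 6.4.1.5:

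- Change "Cardiovascular AEs" to *Cardiovascular AEs by worst intensity*, with a row for subjects with any CV AE, each counted once at worst intensity.
- Add the asterisk to the bullet for drug-related AEs by worst intensity.

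Alternatively, state in the SAP why it departs from protocol 9.3.2 and from Objective 17. If the Core SAP or mock tables already specify intensity for CV AEs, a cross-reference settles the first item.

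Marking the CV AE table for CV history as well would be useful but is optional.

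The cost is two wording edits in each of two sections, one revised table layout and one extra subgroup table per period. The AE data are already collected, and no protocol amendment is needed.

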6.4.1.4 Post-DBT Pre-OL Rimegepant AEs

Frequency tables of post-DBT pre-OL rimegepant AEs are provided for the interim safety analysis set by SOC and PT for the following endpoints:

- AEs by worst intensity
- SAEs.

